6.1.2. Adjustments for Covariates

If there is a statistical difference among treatment groups with respect to baseline characteristics, that variable may be added to the statistical models as a blocking factor or covariate to determine the effect on treatment. Age group and baseline score are planned for inclusion in statistical models, unless otherwise indicated. Age group will be categorized as adolescents (ages 12 to 17 years, inclusive) and adults (≥ 18 years).

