6.1.4. Handling of Dropouts or Missing Data

All possible efforts will be made to ensure that subjects stay in the study and all data are collected as scheduled. Withdrawn subjects will not be replaced. If a substantial number of subjects are withdrawn from the study, the sponsor will evaluate the need for developing replacement criteria. Randomized subjects withdrawn from the study may not reenter.

Missing endpoint values in this study may result from subjects discontinuing from the study prematurely or missing intermediate assessments while remaining on study. To assess the effect of missing data on the primary efficacy analysis, a sensitivity analysis will be performed using multiple imputation (MI) for the Double-blind Period only. Multiple imputations will be used to replace missing IGA outcomes using multiple draws from the posterior predictive distribution estimated from the vehicle treatment. The IGA scores will be imputed and then categorized as treatment success.

Sensitivity analyses to investigate robustness to missing data will be performed for the primary endpoint as described in [Section 8.1.2](#).

Missing safety data and data for secondary endpoints will not be imputed.

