8.1. Primary Efficacy Analysis

8.1.1. Investigator's Global Assessment (IGA)

The 5-point IGA is a measure of disease severity and meets the need for a clinically meaningful measure of success for ichthyosis studies. Each level of severity will consider both the severity of scaling and the severity of roughness. The investigator will rate the subject's condition using the 5-point scale (0-4), excluding the following areas: knees, elbows, neck, palms, soles, axillae, groin, and scalp, where higher scores represent more severe disease. The IGA is collected at all clinic visits. The scoring is as follows below in Table 4.

Table 4: IGA Scoring Definitions

Score	Definition
0	Clear: No scaling and no roughness
1	Almost clear: Occasional fine scales; hardly palpable roughness (mostly smooth)
2	Mild: Small and fine scales predominate; no more than a few large scales; mild roughness on palpation
3	Moderate: Some large scales that may be thick; coarse roughness on palpation
4	Severe: Confluent, primarily large (>1cm) thick scales with plate-like hyperkeratosis

The primary efficacy endpoint is the proportion of subjects in each treatment group who experience successful resolution of LI where “success” is defined as clear/almost clear overall and at least a 2-grade change from Baseline at Day 90/EOT in the Double-blind Period on the 5-point IGA scale. The number and percentage of subjects with treatment success will be summarized by treatment group. The primary efficacy endpoint will be analyzed using a logistic regression model with treatment, baseline IGA score, and age group as factors. The odds ratios and 95% CIs for the odds ratios will be presented. The difference in proportions between the active trifarotene cream HE1 groups and vehicle cream group, 95% CIs for the differences, and *P* values for the differences in treatment will also be presented.

The potential for heterogeneity of treatment effects will be assessed by testing treatment-by-factor interactions. The logistic regression model for the primary analyses will be expanded to include the treatment-by-age group interaction. In the event of quasi or complete separation, the logistic regression model will use Firth’s penalized maximum likelihood estimation.

The same logistic regression model will be used to analyze the proportion of subjects with at least a 50% reduction in IGA score from baseline as a secondary analysis.

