8.1.2. Multiple Imputation

Multiple imputation (MI) of the primary endpoint will be performed as an analysis of sensitivity to missing data in the Double-blind Period only. Following database lock, thorough assessment on the extent of missing data due to COVID-19 will be carried out specifically as pertains to the primary and secondary endpoints. This will inform decisions around reasonability of imputing missing data for secondary endpoints in the Double-blind Period as well. The final determination will be documented in the CSR.

MI assumes that the statistical behavior of drug- and control-treated subjects after discontinuing study drug becomes that of the vehicle group. Multiple-imputations will be used to replace missing IGA outcomes using multiple draws from the posterior predictive distribution estimated from the vehicle treatment group. IGA scores will be imputed and then categorized as treatment success according to Section 8.1.1 above. A placebo-based pattern mixture model (PMM) will be utilized following the steps outlined in Ratitch B and O’Kelly, M.J. (2011)⁴.

Data are processed sequentially by repeatedly calling SAS[®] PROC MI to impute missing outcomes at study visit $t = 1, \dots, T$. The following procedure is followed:

- *Initialization (Step 1)*. Set $t = 0$ (baseline study visit).
- *Iteration (Step 2)*. Set $t = t + 1$. Create a dataset combined records from drug- and vehicle-treated subjects with columns for covariates **X** and outcomes at study visits 1, ..., t with outcomes for all subjects set to missing at study visit t and set to observed or imputed values at study visits 1, ..., $t-1$.
- *Imputation (Step 3)*. Run placebo-based pattern mixture model in SAS[®] PROC MI on this data to impute missing values for study visit t using previous outcomes for study visit 1 to $t-1$ and baseline covariates.
 - Replace imputed data for all subjects at study visit t with their observed values, whenever available. If $t < T$ then go to Step 2, otherwise proceed to Step 4.
 - Repeat steps 1-3, m times with different seed values to create m imputed complete datasets. In this analysis, m will be assigned 50.

- *Analysis (Step 4)*. For each completed dataset use the model as it would have been applied had the data been complete for the continuous outcome. The final inference on treatment difference is conducted from the multiple datasets, as implemented in SAS[®] PROC MI ANALYZE.

The steps for this approach are detailed below:

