[3] Estimates for odds ratio, 95% CI for odds ratio, and P value are from a logistic regression model with treatment, baseline IGA score, and age group as factors. The odds ratio is the estimate of the odds of having successful resolution of LI for subjects treated with Trifarotene cream HE1 relative to that for subjects treated with vehicle. Age group is defined as adolescents (ages 12 to 17 years, inclusive) and adults ≥18 years.

SOURCE: Listing 16.2.6.1

Programming note: If Firth's penalized maximum likelihood is used, add 'Firth's penalized maximum likelihood estimation is used.' to end of 'Note:' footnote. If the treatment-by-age interaction is significant, include it in the logistic regression model and update footnote [3] to include this factor. After Day 90, repeat table for Days 14, 30, and 60.

Table 14.2.1.1.2
Proportion of Subjects with Successful Resolution of LI in the OLE
OLE ITT Population

Study Visit Statistic	Trifarotene cream HE1 200 ug/g (N = XX)
Day 104 n [1] Successful Resolution [2]	XX XX (XX.X%)
Day 120 n [1] Successful Resolution [2]	XX XX (XX.X%)
Day 150 n [1] Successful Resolution [2]	XX XX (XX.X%)
Day 180 n [1] Successful Resolution [2]	XX XX (XX.X%)
Day 194 n [1] Successful Resolution [2]	XX XX (XX.X%)

Abbreviation: CI = confidence interval; EOT = end of treatment; IGA = Investigator's Global Assessment; ITT = intent to treat; LI = Lamellar Ichthyosis; OLE = open label extension.
Note: Percentages are n/Number of subjects in the OLE ITT population within treatment group*100. All subjects received Trifarotene cream HE1 200 ug/g in the OLE. The 5-point (0 - 4) IGA is a measure of disease severity which considers both scaling and roughness. Higher IGA scores represent more severe disease.

[1] Number of subjects with an IGA assessment at each visit.

[2] Number of subjects with successful resolution of LI at a visit. Successful resolution is defined as clear/almost clear overall (IGA of 0 or 1, respectively) and at least a 2-grade change from Baseline on the 5-point (0 - 4) IGA scale. Baseline is defined as the last non-missing assessment recorded prior to the first dose of treatment in the Double-blind Period.

SOURCE: Listing 16.2.6.1

Table 14.2.1.2.1
Primary Analysis, Sensitivity: Logistic Regression Analysis of Successful Resolution of LI
mITT Population

Same shell as Table 14.2.1.1.1

Programming note: Update Abbreviations to remove ITT and include mITT = modified intent-to-treat.

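### A programming note puts a significant treatment-by-age interaction into the primary logistic model, and the odds ratio then reported has no defined meaning

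*SAP*

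**What the plan says.** **Primary model.** SAP Section 8.1.1 says the primary endpoint will be "analyzed using a logistic regression model with treatment, baseline IGA score, and age group as factors". It then turns to heterogeneity: "The potential for heterogeneity of treatment effects will be assessed by testing treatment-by-factor interactions", followed by "The logistic regression model for the primary analyses will be expanded to include the treatment-by-age group interaction". Read in order, the expanded model serves the heterogeneity check.

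**Primary table.** The programming note under the shell of Table 14.2.1.1.1 (Section 14.2) says: "If the treatment-by-age interaction is significant, include it in the logistic regression model and update footnote [3] to include this factor". The shell has one odds-ratio row, filled for each active arm and for the pooled active group, and no rows by age group. Footnote [3] describes the odds ratio as trifarotene-treated subjects relative to vehicle-treated subjects, without reference to age. The note adds a factor to that footnote but does not redefine the odds ratio.

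**Multiple-imputation table.** Table 14.2.1.4 reuses the shell, but its replacement footnote [3] lists main effects only.

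**Covariates.** Section 6.1.2 says: "If there is a statistical difference among treatment groups with respect to baseline characteristics, that variable may be added to the statistical models". No list of variables, test or binding rule is given, and use is not limited to sensitivity analyses.

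**Secondary imputation (a separate matter).** Section 6.1.4: "Missing safety data and data for secondary endpoints will not be imputed". Section 8.1.2, on the assessment of COVID-19 missingness after lock: "This will inform decisions around reasonability of imputing missing data for secondary endpoints in the Double-blind Period as well".

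**The concern.** The text and the table shell do not give the same primary model. Whether the note fires can be known only with treatment codes and outcomes in hand. Once it fires, the treatment coefficient is no longer a common effect. It is the effect in whichever age group is the reference, or an average whose weights follow the coding. The plan names none of these.

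The primary number therefore loses its stated meaning in exactly the case where the age groups appear to differ. The primary and multiple-imputation tables could also rest on different models. The same shell is repeated for Days 14, 30 and 60 and reused for the mITT and PP populations, and the plan does not say whether the switch is decided once or table by table.

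Section 6.1.2 is a lesser fault of the same kind. Under randomization, baseline differences between arms are chance, so testing them is a poor way to choose covariates. Here the choice is left open as well.

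**Working it through.** The plan gives no figure for how the switch behaves, so there is none to reproduce.

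**Inputs from the SAP.** Success rates of 70% active and 40% vehicle, 1:1:1 allocation, and 96 evaluable subjects (3 × 32) (Section 3). 65 enrolled (Section 1). Default two-sided 0.05 level (Section 4.1). Eight baseline variables summarised (Section 7.3).

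**Assumptions.** The adolescent share is not given: 20% and 40% were used under the null, 30% in the effect scenarios. With 65/3 = 21.7 per arm, 20% to 40% means about 4 to 9 adolescents per arm.

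**1. What the odds ratio could be.** Take 70% vs 40% in adults and assume 40% vs 40% in adolescents.
- Adult reference: (0.70/0.30)/(0.40/0.60) = 3.50
- Adolescent reference: (0.40/0.60)/(0.40/0.60) = 1.00
- Equal weighting on the log scale: √(3.50 × 1.00) = 1.87

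**2. How often the switch fires, and its effect on rejection.** Three arms were simulated, with Firth logistic regression throughout, a 2-df Wald test of treatment-by-age at 0.05, and a binary baseline score unrelated to outcome. There were 3,000 trials per null row and 2,000 per effect row. Rejection refers to one active arm vs vehicle.

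| Scenario (vehicle vs active) | N, adolescents | Switch fires | Reject: main effects always | Reject: switch, adult reference | Reject: switch, equal weights |
|---|---|---|---|---|---|
| Null, 40% vs 40% | 65, 20% | 0.1% | 3.7% | 3.8% | 3.7% |
| Null | 65, 40% | 1.7% | 3.3% | 3.6% | 3.3% |
| Null | 96, 20% | 0.7% | 3.9% | 4.0% | 3.8% |
| Null | 96, 40% | 3.1% | 3.7% | 4.4% | 3.7% |
| 40% vs 70% in both age groups | 65, 30% | 0.7% | 42.6% | 42.6% | 42.5% |
| 40% vs 70% in adults only | 65, 30% | 6.4% | 23.9% | 26.8% | 22.5% |
| 40% vs 85% in adolescents only | 65, 30% | 7.3% | 11.1% | 11.6% | 11.8% |

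The largest rise in type I error is 4.37% − 3.73% = 0.64 points.

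**3. What happens when it fires.**
- Effect in adults only (0.0635 × 2,000 = 127 trials): the median odds ratio is 2.49 from main effects, 8.16 at the adult reference and 1.52 with equal weights. The 8.16 overshoots the true adult value of 3.50 because these trials are selected on a significant interaction. The significance verdict differs from the main-effects model in 47% (adult reference) or 24% (equal weights) of them. Over all trials that is 0.0635 × 0.465 = 3.0% or 0.0635 × 0.244 = 1.5%.
- Effect in adolescents only (0.0725 × 2,000 = 145 trials): the medians are 1.53, 0.44 and 3.47, so the coding decides even the direction.

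**4. Baseline trigger.** Of the eight variables, baseline IGA and age (as age group) are already in the model, which leaves six. If each is tested at 5% and the tests are independent, the chance of at least one flag is 1 − 0.95^6 = 0.265, about 26%. Height, weight and BMI are correlated; with four effective tests it is 1 − 0.95^4 = 0.185, about 19%.

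**The case against.** The strongest defence is that the plan does write down a default primary model, and that the switch is a stated conditional rule in a document to be filed before any unblinded analysis. Section 4.1 supplies a 0.05 level and Section 8.1.1 supplies Firth estimation for separation. Success counts and percentages by arm do not depend on the model. All of this stands.

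A reader might infer that the whole primary model is picked from unblinded results and that the nominal P value is therefore invalid. The documents do not support that. The rule is data-adaptive but prespecified, and simulated type I error stayed below 5% throughout. Confidence-interval coverage was not examined. A reader might also expect the switch to fire in 5% of null trials. The simulated rate was 0.1% to 3.1%, because the Firth Wald test is conservative in these sparse cells. The SAP invokes Firth only under separation, so the rate with ordinary maximum likelihood could differ.

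On Section 6.1.2, the wording is permissive, the trigger uses treatment codes and baseline data but not outcomes, and the stated purpose can be read as a supportive check. Counting all eight variables would give 1 − 0.95^8 = 34%, but two are already adjusted for. What remains is that the text does not confine the step to sensitivity analyses.

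Finally, the two statements on secondary imputation might be read as further evidence against the primary model. They are not. They concern secondary endpoints only, and Sections 3.6 and 4.2 place unblinding after lock, so a decision after lock is not necessarily an unblinded one.

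**Conclusion.** The point holds for the note under Table 14.2.1.1.1 set against Section 8.1.1. When the switch fires, the primary table shows an odds ratio that the plan does not define, under a footnote that still describes the overall comparison, and possibly from a different model than the multiple-imputation table.

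The fault is rare under the null but material when it occurs: the same planning assumptions give 3.50, 1.00 or 1.87, and up to about half of the significance verdicts in switched trials change. These sizes rest on the assumed adolescent share and on assumed adolescent success rates. The undefined odds ratio follows from the text alone. Damage to error control is small.

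Section 6.1.2 is a secondary fault. The conflict between Sections 6.1.4 and 8.1.2 is real but has no bearing on the primary odds ratio. The change should be made.

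**What to change.** 1. In Section 8.1.1, state that the primary odds ratio, CI and P value always come from the main-effects model with treatment, baseline IGA score and age group, whatever the interaction test shows.
2. Delete the interaction sentence from the note under Table 14.2.1.1.1. This also removes the mismatch with Table 14.2.1.4 and the question of whether each visit or population switches separately.
3. Report the interaction P value and age-specific estimates as supportive, in their own rows or table.
4. In Section 6.1.2, limit covariates added because of baseline imbalance to a labelled sensitivity analysis.
5. Separately, reconcile Section 6.1.4 with Section 8.1.2. Either keep the statement that secondary endpoints are not imputed, or take the decision at the blinded review before lock that Section 7.2 already provides for.

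The cost is a few edited sentences and no data. With a common effect, the simulated rejection rate is unchanged (42.6% vs 42.5% to 42.6%). With an effect in adults only, the fixed model rejects in 23.9% of trials against 26.8% under the adult-reference reading, but the latter partly tests a different hypothesis.

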14.3. Planned Listing Shells

Listing 16.2.1
Subject Disposition
All Subjects

Randomized Treatment: XXXXXXXXX

Subject ID	Date Informed Consent Signed	Subject Status	Double-blind Period			OLE		
			Date of Completion/Discontinuation (Study Day)	Reason for Early Termination	Was the Blind Broken For This Subject?	Date of Completion/Discontinuation (Study Day)	Reason for Early Termination	
XXXXXX	DDMMYYYY	XXXXXX	DDMMYYYY (XX)			XXXXXX	DDMMYYYY (XX)	
XXXXXX	DDMMYYYY	XXXXXX	DDMMYYYY (XX)			XXXXXX	DDMMYYYY (XX)	
XXXXXX	DDMMYYYY	XXXXXX	DDMMYYYY (XX)	XXXXXXXX: XXXXXX		XXXXXX	DDMMYYYY (XX)	XXXXXXXX: XXXXXX
XXXXXX	DDMMYYYY	XXXXXX	DDMMYYYY (X)	XXXXXX		XXXXXX	DDMMYYYY (X)	XXXXXX
XXXXXX	DDMMYYYY	XXXXXX	DDMMYYYY (XX)	XXXXXXXXXXXXXXXX	XXX; XXXXXX; XXXXX	XXXXXX	DDMMYYYY (XX)	XXXXXXXXXXXXXXXX

Abbreviation: OLE = open label extension.

Note: Subjects were randomized to either Trifarotene cream HE1 100 ug/g, Trifarotene cream HE1 200 ug/g, or vehicle in the double-blind period. All subjects received Trifarotene cream HE1 200 ug/g in the open label extension period. Study day is calculated relative to the date of first dose of study drug.

Programming Note: Subject status will be completed continuing, completed not continuing, or early termination. If reason for early termination is AE, Physician Decision, Protocol Violation, or Other, concatenate the specify text as follows: "Other: XXXXXXXXX". If reason for early termination is lost to follow-up, concatenate with date of last contact and comments as follows: "Lost to follow-up; date of last contact: DDMMYYYY; XXXXX". If reason for early termination is death, concatenate with comment, cause of death and date of death as follows: "Lost to follow-up; XXXXX; date of death: DDMMYYYY; comment: XXXX".

Listing 16.2.2.1
 Inclusion and Exclusion Criteria
 All Subjects

Randomized Treatment: XXXXXXX

Subject ID	Assessment Date (Study Day)	Met All Inclusion Criteria?	Inclusion Criteria Number(s) Not Met [1]	Met Any Exclusion Criteria?	Exclusion Criteria Number(s) Met [2]
XXXXXX	DDMMMYYYY (XX)	Yes		No	
XXXXXX	DDMMMYYYY (XX)	Yes		No	
XXXXXX	DDMMMYYYY (XX)	Yes		No	
XXXXXX	DDMMMYYYY (XX)	No	XX	No	
XXXXXX	DDMMMYYYY (XX)	Yes		No	
XXXXXX	DDMMMYYYY (XX)	Yes		Yes	XX; XX

Note: Subjects were randomized to either Trifarotene cream HE1 100 ug/g, Trifarotene cream HE1 200 ug/g, or vehicle in the double-blind period. All subjects received Trifarotene cream HE1 200 ug/g in the open label extension period. Study day is calculated relative to the date of first dose of study drug.

[1] XX = XXXXXXXXXXXXXXXXXXXXXXXX.

[2] XX = XXXXXXXXXXXXXXXXXXXX; XX = XXXXXXXXXXXXXXXXXXXXXXXX.

Programming note: If more than 1 inclusion or exclusion criterion number exists, concatenate with a comma as shown above. Decode any relevant criteria in the footnotes as shown in the example. If no criteria are present for a column, remove the [1] and/or [2] from the column header.

Listing 16.2.2.2
 Screen Failures
 All Subjects

Subject ID	Date of Screen Failure (Study Day)	Reason for Screen Failure	Other Reason for Screen Failure
XXXXXX	DDMMYYYY (XX)	XXXXXX	XXXXXXXXXXXXXXXXXX
XXXXXX	DDMMYYYY (XX)	XXXXXX	
XXXXXX	DDMMYYYY (XX)	XXXXXX	
XXXXXX	DDMMYYYY (XX)	XXXXXX	XXXXXXXXXXXXXXXXXX
XXXXXX	DDMMYYYY (XX)	XXXXXX	
XXXXXX	DDMMYYYY (XX)	XXXXXX	

Note: Subjects were randomized to either Trifarotene cream HE1 100 ug/g, Trifarotene cream HE1 200 ug/g, or vehicle in the double-blind period. All subjects received Trifarotene cream HE1 200 ug/g in the open label extension period. Study day is calculated relative to the date of first dose of study drug.

Listing 16.2.2.3
Protocol Deviations
All Subjects

Randomized Treatment: XXXXXXXXXXXX

Subject ID	Date Identified (Study Day)	Event Date (Study Day)	Study Visit	Event Type	Violation Level	Description	Action/Resolution	Reportable to IRB?	Excluded from PP Population?
XXXXXX	DDMMYYYYY	DDMMYYYYY	XXXXXX	XXXXXXXXXXXX	MAJOR	XXXXXX	XXXXXX	XXX; DDMMYYYYY; XXXXX	XXX
	(XX)	(XX)							
	DDMMYYYYY	DDMMYYYYY	XXXXXX	XXXXXXXXXXXX	MINOR	XXXXXXXXXXXX	XXXXXXXXXXXX		XXX
	(XX)	(XX)							
XXXXXX	DDMMYYYYY	DDMMYYYYY	XXXXXX	XXXXXXXXXXXX	MINOR	XXXXXXXXXXXX	XXXXXXXXXXXX		XX
	(XX)	(XX)							
XXXXXX	DDMMYYYYY	DDMMYYYYY	XXXXXX	XXXXXXXXXXXX	MAJOR	XXXXXXXXXXXX	XXXXXXXXXXXX		XX
	(X)	(X)							

Abbreviation: IRB = institutional review board; PP = per protocol.

Note: Subjects were randomized to either Trifarotene cream HE1 100 ug/g, Trifarotene cream HE1 200 ug/g, or vehicle in the double-blind period. All subjects received Trifarotene cream HE1 200 ug/g in the open label extension period. Study day is calculated relative to the date of first dose of study drug.

Programming note: the structure of this listing may change depending on the information in the protocol deviations file. If Reportable to IRB is yes, concatenate IRB Submission Date and IRB Submission Comments fields with a semicolon.

Listing 16.2.3
Analysis Populations
All Subjects

Subject ID	Randomization			Actual Treatment	Analysis Populations					Primary Reason(s) for Exclusion
	Date	Number	Treatment		ITT/OLE ITT [1]	mITT/OLE mITT [2]	PP/OLE PP [3]	Safety/OLE Safety [4]	PK [5]	
XXXXXX	DDMMYYYY	XXXX	XXXXXXXXXXXX	XXXXXXXXXXXX	Yes	Yes	No	Yes	No	PP: Subject had a significant protocol violation.
XXXXXX	DDMMYYYY	XXXX	XXXXXXXXXXXX	XXXXXXXXXXXX	Yes	Yes	Yes	Yes	Yes	
XXXXXX	DDMMYYYY	XXXX	XXXXXXXXXXXX	XXXXXXXXXXXX	No	Yes	No	Yes	No	Safety: Subject did not receive at least one application of study drug.

Abbreviations: ITT = intent-to-treat; mITT = modified intent-to-treat; OLE = open label extension; PK= pharmacokinetic; PP = per protocol.

Note: Subjects were randomized to either Trifarotene cream HE1 100 ug/g, Trifarotene cream HE1 200 ug/g, or vehicle in the double-blind period. All subjects received Trifarotene cream HE1 200 ug/g in the open label extension period.

[1] The ITT population includes all randomized subjects. The OLE ITT population includes all subjects who complete the 90-day Double-blind Treatment Period and sign the OLE informed consent.

[2] The mITT includes all subjects in the Safety population with at least 1 post baseline assessment of efficacy in the Double-blind Period. The OLE mITT population includes all subjects in the OLE Safety population with at least 1 assessment of efficacy after Visit 6.

[3] The PP Population includes subjects in the mITT population who met all inclusion criteria and no exclusion criteria, were compliant with study drug application, and who had no significant protocol deviations. The OLE PP population includes all subjects in the OLE mITT population who met all inclusion criteria and no exclusion criteria, were compliant with study drug application from baseline through EOT, and who had no significant protocol deviations throughout the study.

[4] The Safety Population includes all subjects who are randomized to treatment and receive at least 1 application of study drug in the Double-blind Period. The OLE Safety population includes all subjects who complete the 90-day Double-blind Treatment Period and receive at least 1 application of study drug in the OLE.

[5] The PK Population includes all subjects in the Safety population who have at least 1 plasma sample with quantifiable concentration.

Programming note: Concatenate all reasons for exclusion with a colon.

Listing 16.2.4.1
 Subject Demographics
 All Subjects

Randomized Treatment: XXXXXXXX										
Subject ID	Date of Birth	Age (years)	QOL Questionnaires Used	Sex	Child-Bearing Potential?	Ethnicity	Race	Weight (kg)	Height (cm)	BMI (mg/m ²) [1]
XXXXXX	DDMMYYYY	XX	XXXX	XXXX	No	XXXXXXXX	XXXXXXXX	XX.X	XX.X	XX.X
XXXXXX	DDMMYYYY	XX	XXXXXX	XXXXXX	No	XXXXXXXX	XXXXXX	XX.X	XX.X	XX.X
XXXXXX	DDMMYYYY	XX	XXXXXX	XXXXXX	Yes	XXXXXXXX	XXXXXX	XX.X	XX.X	XX.X
XXXXXX	DDMMYYYY	XX	XXXX	XXXX	No	XXXXXXXX	XXXXXX	XX.X	XX.X	XX.X
XXXXXX	DDMMYYYY	XX	XXXXXX	XXXXXX	No	XXXXXXXX	XXXXXX	XX.X	XX.X	XX.X
XXXXXX	DDMMYYYY	XX	XXXX	XXXX	Yes	XXXXXX	XXXXXX	XX.X	XX.X	XX.X

Abbreviations: BMI = body mass index; QOL =quality of life.

Note: Subjects were randomized to either Trifarotene cream HE1 100 ug/g, Trifarotene cream HE1 200 ug/g, or vehicle in the double-blind period. All subjects received Trifarotene cream HE1 200 ug/g in the open label extension period. Height and weight are values obtained at screening.

[1] BMI = weight (kg) / [height (m)]².

Listing 16.2.4.2
Informed Consent and Reconsent
All Subjects

Randomized Treatment: XXXXXXXXXXXX

Subject ID	Screened Previously?	Previous Subject Number	Protocol Version of Initial Consent/Assent	Date Informed Consent/Assent Signed	Consent to PK Sub-study?	Signed Photographic ICF?	Re-consent to Later Protocol Version 2.0?	Date Reconsent	Date of Assent	Date OLE Informed Consent/Assent Signed
XXXXXX	No		X.X	DDMMYYYY	No	No	Yes	DDMMYYYY	DDMMYYYY	DDMMYYYY
XXXXXX	No		X.X	DDMMYYYY	No	No	Yes	DDMMYYYY	DDMMYYYY	DDMMYYYY
XXXXXX	Yes	XXXXXXXX	X.X	DDMMYYYY	Yes	Yes	Yes	DDMMYYYY	DDMMYYYY	DDMMYYYY
XXXXXX	No		X.X	DDMMYYYY	No	No	Yes	DDMMYYYY	DDMMYYYY	DDMMYYYY
XXXXXX	No		X.X	DDMMYYYY	No	No	Yes	DDMMYYYY	DDMMYYYY	DDMMYYYY
XXXXXX	Yes	XXXXXXXX	X.X	DDMMYYYY	Yes	Yes	Yes	DDMMYYYY	DDMMYYYY	DDMMYYYY

Abbreviations: ICF = informed consent form; OLE =open label extension; PK = pharmacokinetic.

Note: Subjects were randomized to either Trifarotene cream HE1 100 ug/g, Trifarotene cream HE1 200 ug/g, or vehicle in the double-blind period. All subjects received Trifarotene cream HE1 200 ug/g in the open label extension period.

Listing 16.2.4.3
 Medical History
 All Subjects

Randomized Treatment: XXXXXXXXXXXXXXXXX

Subject ID	System Organ Class/ Preferred Term/ Verbatim Term	Start Date (Study Day)/ End Date (Study Day)
XXXXXX	XXXXXXXXXXXXXXXXX/ XXXXXXXXXXXXXXXXX/ XXXXXXXXXXXXXXXXX	DDMMYYYY (X)/ DDMMYYYY (X)
	XXXXXXXXXXXXXXXXX/ XXXXXXXXXXXXXXXXX/ XXXXXXXXXXXXXXXXX	--MMYYYY/ Ongoing
	XXXXXXXXXXXXXXXXX/ XXXXXXXXXXXXXXXXX/ XXXXXXXXXXXXXXXXX	DDMMYYYY (X)/ Ongoing
XXXXXX	XXXXXXXXXXXXXXXXX/ XXXXXXXXXXXXXXXXX/ XXXXXXXXXXXXXXXXX	DDMMYYYY (X)/ DDMMYYYY (X)

Abbreviation: MedDRA = Medical Dictionary for Regulatory Activities.

Note: Subjects were randomized to either Trifarotene cream HE1 100 ug/g, Trifarotene cream HE1 200 ug/g, or vehicle in the double-blind period. All subjects received Trifarotene cream HE1 200 ug/g in the open label extension period. Study day is calculated relative to the date of first dose of study drug. Medical history was coded using MedDRA version 21.1. Only subjects with any medical history recorded are listed.

Programming note: SOC & PT text should be in title case in table.

Listing 16.2.5.1
 Initial Study Drug Application
 All Subjects

Randomized Treatment: XXXXXXXXXXXXXXXXXXXX

Subject ID	Was Study Drug Applied?	Date of Application (Study Day)	Time of Administration	Tube Weight Before Drug Application (grams)	Tube Weight After Drug Application (grams)	Amount Used (grams)
XXXXXX	XXX	DDMMYYYY (X)	HH:MM (X)	XXX	XXX	XXX
XXXXXX	XX; XXXXX					
XXXXXX	XXX	DDMMYYYY (X)	HH:MM (X)	XXX	XXX	XXX

Note: Subjects were randomized to either Trifarotene cream HE1 100 ug/g, Trifarotene cream HE1 200 ug/g, or vehicle in the double-blind period. All subjects received Trifarotene cream HE1 200 ug/g in the open label extension period. Study day is calculated relative to the date of first dose of study drug.

Programming Note: *If drug was not applied, concatenate reason in cell with a semicolon.*

Listing 16.2.5.2
 Drug Accountability (Dispensed and Returned)
 All Subjects

Randomized Treatment: XXXXXXXXXXXXXXXXXXXX

Subject ID	Study Visit	Was Study Drug Dispensed at this Visit?	Dispensation Date (Study Day)	Tube Weight of Tubes Dispensed (grams)	Kit ID Dispensed	Was Study Drug Returned at this Visit?	Return Date (Study Day)	Number of Tubes Returned	Number of Tubes Returned Unused	Tube Weight of Tubes Returned (grams)	Kits Returned
XXXXXX	XXXXXX	XXX	DDMMYYYY (X)	XXX	XXX	XXX	DDMMYYYY (X)	XXX	XXX	XXX	XXX
XXXXXX	XXXXXX	XX; XXXXX				XX; XXXXX					
XXXXXX	XXXXXX	XXX	DDMMYYYY (X)	XXX	XXX	XXX	DDMMYYYY (X)	XXX	XXX	XXX	XXX

Note: Subjects were randomized to either Trifarotene cream HE1 100 ug/g, Trifarotene cream HE1 200 ug/g, or vehicle in the double-blind period. All subjects received Trifarotene cream HE1 200 ug/g in the open label extension period. Study day is calculated relative to the date of first dose of study drug.

Programming Note: If drug was not dispensed/returned at a visit, concatenate reason in cell with a semicolon.

Listing 16.2.5.3
 Subject Diary
 All Subjects

Randomized Treatment: XXXXXXXXXXXXXXXXXXXX

Subject ID	Study Visit	Was Diary Data Collected at this Visit?	Dose Number	Date of Dose (Study Day)	Day of the Week	Time Drug Taken	Areas of Skin Treated	Areas Not Treated	Reasons	Cream Reaction
XXXXXX	XXXXXX	XXX	XX	DDMMYYYY (X)	XXXXXXXX	HH:MM	XXXXXXXX	XXXXXXXX	XXXXXXXX	XXXXXXXX
								XXXXXXXX	XXXXXXXX	XXXXXXXX
XXXXXX	XXXXXX	XX; XXXXX								
XXXXXX	XXXXXX	XXX	XX	DDMMYYYY (X)	XXXXXX	HH:MM	XXXXXXXX	XXXXXXXX	XXXXXXXX	XXXXXXXX
								XXXXXXXX	XXXXXXXX	XXXXXXXX
								XXXXXXXX	XXXXXXXX	XXXXXXXX

Note: Subjects were randomized to either Trifarotene cream HE1 100 ug/g, Trifarotene cream HE1 200 ug/g, or vehicle in the double-blind period. All subjects received Trifarotene cream HE1 200 ug/g in the open label extension period. Study day is calculated relative to the date of first dose of study drug.

Programming Note: If diary data was not collected at this visit, concatenate reason in cell with a semicolon. Include all body areas not treated. If body area not treated or reason is other, concatenate specify field in cell with a semicolon.

Listing 16.2.5.4.1
 Pharmacokinetic Sample Collection
 PK Population

Randomized Treatment: XXXXXXXXXXXXXXXXXXXX

Subject ID	Was the Sample Collected?	Reason	Date Collected (Study Day)
XXXXXX	XXXXXXX	XXXXXXX	DDMMYYYY (X)
	XXXXXXX	XXXXXXX	DDMMYYYY (X)
	XXXXXXX	XXXXXXX	DDMMYYYY (X)
	XXXXXXX	XXXXXXX	DDMMYYYY (X)
XXXXXX	XXXXXXX	XXXXXXX	DDMMYYYY (X)

Abbreviation: PK = pharmacokinetic.

Note: Subjects were randomized to either Trifarotene cream HE1 100 ug/g, Trifarotene cream HE1 200 ug/g, or vehicle in the double-blind period. All subjects received Trifarotene cream HE1 200 ug/g in the open label extension period. Study day is calculated relative to the date of first dose of study drug.

Listing 16.2.5.4.2
 Pharmacokinetic Sample Collection (Substudy)
 PK Population

Randomized Treatment: XXXXXXXXXXXXXXXXXXXX

Subject ID	Initial Study Drug Application?	Date Collected (Study Day)	Time	Timepoints	Sample Collected?	Date/Time Collected (Study Day)
XXXXXX	XXX	DDMMYYYY (X)	HH:MM	XXXXXXX	XXX	DDMMYYYY/HH:MM (X)
	XXX	DDMMYYYY (X)	HH:MM	XXXXXXX	XXX	DDMMYYYY/HH:MM (X)
	XX	DDMMYYYY (X)	HH:MM	XXXXXXX	XXX	DDMMYYYY/HH:MM (X)
	XX	DDMMYYYY (X)	HH:MM	XXXXXXX	XXX	DDMMYYYY/HH:MM (X)
XXXXXX	XX	DDMMYYYY (X)	HH:MM	XXXXXXX	XXX	DDMMYYYY/HH:MM (X)

Abbreviation: PK = pharmacokinetic.

Note: Subjects were randomized to either Trifarotene cream HE1 100 ug/g, Trifarotene cream HE1 200 ug/g, or vehicle in the double-blind period. All subjects received Trifarotene cream HE1 200 ug/g in the open label extension period. Study day is calculated relative to the date of first dose of study drug.

Programming Note: If sample was not collected, concatenate reason in cell with a semicolon.

Listing 16.2.5.4.3
 Pharmacokinetic Concentrations
 PK Population

Randomized Treatment: XXXXXXXXXXXXXXXXXXXX

Subject ID	Study Visit	Time In-Clinic Dose Taken	Time Point	Was Sample Collected?	Date/Time Sample Collected (Study Day)	Concentration (unit)
XXXXXX	XXXXXX	HH:MM	XXXXXX	Yes	DDMMYYYY/HH:MM (X)	X.XX
	XXXXXX	HH:MM	XXXXXX	Yes	DDMMYYYY/HH:MM (X)	X.XX
	XXXXXX	HH:MM	XXXXXX	Yes	DDMMYYYY/HH:MM (X)	X.XX
	XXXXXX	HH:MM	XXXXXX	No; XXXXXXXX		
XXXXXX	XXXXXX	HH:MM	XXXXXX	Yes	DDMMYYYY/HH:MM (X)	X.XX

Abbreviation: BLQ = below the limit of quantification; PK = pharmacokinetic.

Note: Subjects were randomized to either Trifarotene cream HE1 100 ug/g, Trifarotene cream HE1 200 ug/g, or vehicle in the double-blind period. All subjects received Trifarotene cream HE1 200 ug/g in the open label extension period. Study day is calculated relative to the date of first dose of study drug. Any results that are BLQ (i.e., <0.xx) are displayed as BLQ in the listing.

Listing 16.2.5.4.4
Pharmacokinetic Calculated Parameters
PK Population

Randomized Treatment: XXXXXXXXX

Subject ID	AUC _{0-t} (unit)	C _{max} (unit)	T _{max} (unit)	AUC _{0-inf} (unit)	t _{1/2} (unit)	λ _z (unit)
XXXXX	X.XX	X.XX	X.XX	X.XX	X.XX	X.XX
XXXXX	X.XX	X.XX	X.XX	X.XX	X.XX	X.XX

Abbreviation: AUC = area under the plasma concentration-time curve; C_{max} = peak plasma concentration; CV = coefficient of variation; λ_z = apparent terminal phase rate constant. PK = pharmacokinetic; SD = standard deviation; t_{1/2} = first order termination half-life; T_{max} = time of C_{max}.

Note: Subjects were randomized to either Trifarotene cream HE1 100 ug/g, Trifarotene cream HE1 200 ug/g, or vehicle in the double-blind period. All subjects received Trifarotene cream HE1 200 ug/g in the open label extension period. Study day is calculated relative to the date of first dose of study drug. 0-t represents time from 0 to the time of the last quantifiable plasma concentration.

Programming note: the number of decimal places depends on the raw data. The above parameters are expected, however the final parameters provided by the pharmacokineticist will be listed.

Listing 16.2.6.1
Investigator's Global Assessment (IGA)
All Subjects

Randomized Treatment: XXXXXXXXXXXXXXXXX

Subject ID	Was Assessment Performed?	Study Visit	Assessment Date (Study Day)	Body Area [1]	Result	Baseline [2]	CFB [3]	% CFB [4]	Successful Resolution of LI?
XXXXXX	XXX	XXXXXX	DDMMYYYY (XX)	XXXXXX	X	X	X	X	XXX
				XXXXXX	X	X	X	X	XX
XXXXXX	XXX	XXXXXX	DDMMYYYY (XX)		X	X	X	X	XXX
					XX	XX	XX	XX	XX
					XX	XX	XX	XX	XXX
					XX	XX	XX	XX	XXX
XXXXXX	XX; XXXXX								

Abbreviations: CFB = change from baseline; IGA = Investigator's Global Assessment; LI = Lamellar Ichthyosis.

Note: Subjects were randomized to either Trifarotene cream HE1 100 ug/g, Trifarotene cream HE1 200 ug/g, or vehicle in the double-blind period. All subjects received Trifarotene cream HE1 200 ug/g in the open label extension period. Study day is calculated relative to the date of first dose of study drug. The 5-point (0 - 4) IGA is a measure of disease severity which considers both scaling and roughness. Higher IGA scores represent more severe disease. Successful resolution is defined as clear/almost clear overall and at least a 2-grade change from Baseline on the 5-point (0 - 4) IGA scale.

[1] Body area only for subjects enrolled under protocol version 1.0.

[2] Baseline is defined as the last non-missing assessment recorded prior to the first dose of treatment in the Double-blind Period.

[3] CFB is calculated as Result - Baseline.

[4] % CFB is calculated as Change from baseline / Result at baseline * 100.

Programming note: If assessment was not performed, concatenate reason with a semicolon. CFB, % CFB and Successful Resolution of LI columns will not be populated for Baseline rows.

Listing 16.2.6.2
 Visual Index for Ichthyosis (VIIS)
 All Subjects

Randomized Treatment: XXXXXXXXXXXXXXXXX

